Trial of PermaNet 3-barrier bednets as part of an operational distribution programme in Haut-Katanga province, DRC (BBnets)

Study protocol v2.2 29/02/24

amendments made to:

sections referring to multiple collection periods (there will only be one 3 month epidemiological data collection period and) one entomological collection period and the total data collection period will be up to 5 months rather than 7 months

bioavailability testing removed

Revised timeline added

A two-armed cluster randomised trial comparing PermaNet 3 with PermaNet 3-barrier bednets (P3-BBnets) is presented associated with a programmatic distribution of bednets in Haut Katanga province, southern DRC, which has taken place according to our specified distribution plan in May-June 2023. BBnets are identical to PermaNet 3 except for the addition of a longitudinal upright barrier, which contains the same ingredients (deltamethrin and PBO) as the roof of a PermaNet 3, and significantly enhances insecticide resistant mosquito killing capacity. The study will take place within health zones of the Lubumbashi area of Haut Katanga. Health areas within the health zones are randomised to receive the 300,000 P3-BBnets available, with all others receiving PermaNet 3. Training in hanging instructions for BBnets were provided to community health workers, who performed household distribution of all nets and additional hanging materials for the BBnets, which the trial team have supplied. The primary outcome variable for the study is prevalence of malaria recorded by routine testing of visitors at their first ante-natal clinics (ANC1), which provides an efficient and economical method for data collection. Visitors will be recruited by health centre staff to give their permission to take a rapid diagnostic test (RDT) for malaria and will be treated with artemisinin combination therapy (ACT) if positive; they will also be asked to complete a short questionnaire. All 21 health areas receiving P3-BBnets will be monitored for ANC1 malaria prevalence, as well as 42 areas receiving PermaNet 3. This design provides power to detect a 25% reduction in malaria prevalence attributable to P3-BBnets compared to PermaNet 3 as a reference. Data will be recorded over a continuous survey period of 3 months within the first year after distribution, during which surveys to characterise the malaria mosquito vector community and their insecticide resistance will also be performed, along with assessments of the hanging of bednets and questionnaires to assess user perceptions of the nets they have received. The physical and chemical integrity of nets, and their bioefficacy will also be assessed.

Funding and support

Nets have been provided by Vestergaard and AMF. Funding for the trial is available from ERDF and UKRI-SIPF awards to LSTM. SANRU and the PNLP are providing support for the programmatic distribution. Ethical permission and sponsorship will be provided by LSTM, and ethical permission from University of Kinshasa.

Lay summary

Background

Performance of insecticide impregnated nets treated with pyrethroid insecticide is challenged by widespread pyrethroid resistance in *Anopheles* malaria vectors. New generation nets combine an additional insecticide or resistance-blocking molecule 'PBO' to combat resistance, but a more novel approach is to modify the physical design of the bednet to increase capacity to kill mosquitoes. LSTM have designed a patented barrier bednet, which adds an 40cm upright longitudinal section hanging above the roof of the bednet. The barrier intercepts mosquitoes during their typical flight paths when seeking to blood feed from sleepers under nets, increasing mosquito-net/insecticide contact. In partnership with the bednet producers, providers, distributors and malaria control programme bednets have been produced which are identical to the successful and widely distributed PermaNet 3, but with the added barrier, which incorporates both pyrethroid insecticide and PBO present on the roof of a PermaNet 3. In laboratory tests, these 'P3-BBnets' are shown to kill significantly more insecticide resistant mosquitoes than unmodified PermaNet 3, but the impact of P3-BBnets on malaria prevention has yet to be tested.

Overall Aim

The overall aim of the project is to evaluate the capacity of P3-BBnets to prevent malaria in comparison to unmodified PermaNet 3, in a cluster randomised trial as part of a programmatic distribution of bednets in Haut Katanga, Democratic Republic of Congo (DRC). Entomological surveillance will involve collections to characterise the *Anopheles* vector community and insecticide resistance profiles.

Methods in Brief

300,000 P3-BBnets are provided as part of a programmatic distribution of approximately 4.5 M bednets to Haut Katanga province, with health areas within the city of Lubumbashi randomly allocated to receive P3-BBnets, with all others receiving PermaNet 3. In common with a recent LSTM- and University of Kinshasa-led trial in Sud Ubangi province, DRC, the primary outcome measured will be malaria prevalence in consenting women attending their first antenatal clinic appointment, during which they receive a malaria test and receive artemisinin combination treatment if positive, and complete a short questionnaire to assess bednet possession and usage. The study design is capable of detecting a 25% reduction in malaria in P3-BBnets vs. P3, within an overall 12-month window after net distribution. One round of entomological collections will characterise the malaria vector community and perform insecticide resistance testing. We will also gather information via questionnaires on bednet use and perceptions from randomly-selected households and we will also collect a sample of bednets from houses to assess their physical and chemical durability and capacity to kill mosquitoes.

Index

- i. List of Abbreviations
- ii. Glossary

1. Background

- 1.1 Insecticide treated bednets: standard and new generation
- 1.2 Barrier bednets
- 1.3 Trial designs for comparative assessment of bednets
 - 1.3.1 Antenatal clinic-based assessment of malaria prevalence
 - 1.3.2 Malaria and bednet distributions in DRC

2. Study design

- 2.1 Overview of the operational cRCT BBnet trial
- 2.2 Justification for the research
- 2.3 Study setting
- 2.4 Sample size
- 2.5. Cluster allocation and bednet distribution
 - 2.5.1 Health area enrolment
 - 2.5.2 Training

3. Recruitment

- 3.1 ANC clinic visitors
- 3.2 Household surveys

4. Study Outcome Variables

- 4.1 ANC1 malaria prevalence
 - 4.1.1 Recording periods and baseline data
 - 4.1.2 Secondary epidemiological outcome

1.1 Insecticide treated bednets: standard and new generation

Distribution of long-lasting insecticide impregnated nets (LLINs) has been the basis of malaria prevention in Africa, accounting for the majority of the reduction in disease prevalence seen over the last two decades. LLINs work by protecting the individual who sleeps under the net, but crucially also protecting the community in which the nets are distributed by killing the mosquitoes that try and feed on individuals sleeping under the net. Pyrethroid resistance in Anopheles malaria vectors is now widespread across Africa and evidence suggests that pyrethroid resistance can impact the effectiveness of LLINs (Protopopoff et al. 2018). Whilst nets remain in good condition, personal protective efficacy can persist because the LLIN still acts as a physical barrier to stop biting, but the community effect from mosquito mortality is lost where resistance frequency and level are high. Despite concerns over the impact of pyrethroid resistance, standard pyrethroid-only nets remain widely distributed, primarily owing to their low cost and the aim of programmes to provide universal coverage of nets (at least one per two sleepers) on limited budgets. However, newer dual-treated nets are increasingly distributed following recent trial successes, some incorporating a second insecticide such as chlorfenapyr, Interceptor G2 (Mosha et al. 2022; Accrombessi et al. 2023) alongside pyrethroid or an insecticide synergist piperonyl butoxide (PBO) plus pyrethroid, which acts to block metabolic resistance enzymes which can cause pyrethroid resistance (Protopopoff et al. 2018; Staedke et al. 2020). The basic cost of manufacturing these nets, especially IG2 nets, is higher than pyrethroid-only nets, increasing costs of mass distribution campaigns. In addition, the volume of next-generation LLINs that can be manufactured to order may also be limited by insecticide availability, creating problems for timing of distribution programmes.

1.2 Barrier bednets

An alternative way in which LLIN effectiveness could be enhanced is by altering the design of the net to increase capacity to kill mosquitoes as they seek human hosts for blood-feeding. A design developed at the Liverpool School of Tropical Medicine provides such a design modification and exploits the characteristic behaviour of *Anopheles* malaria vectors to traverse the roof of a bednet seeking entry whilst often making limited contact with the net roof (Parker et al. 2015, 2017). Addition of a small vertical barrier above the roof of the net intercepts mosquitoes during their flight paths, increasing their contact with the net and its active ingredients. Laboratory trials at LSTM and experimental hut trials in Burkina Faso have shown such 'barrier bednets' (BBnets) significantly increase mortality of pyrethroid resistant mosquitoes, with modelling predicting substantial additional protective benefit against malaria (Murray et al. 2020). The BBnet design is patented and requires minimal change from existing LLIN manufacturing processes and limited behavioural change by users. BBnets offer a rapid, safe, and affordable method to extend LLIN lifespan in the fight against malaria. However, epidemiological effectiveness of BBnets has yet to be assessed.

Following experimental work and mathematical modelling to explore shape and treatment options, in collaboration with the leading net manufacturer Vestergaard, LSTM developed a BBnet ready for evaluation in a field trial. Essentially, the design is a PermaNet 3 (P3) bednet with a vertical barrier made from the same material as the P3 roof (Fig. 1). PermaNet 3 is a long-lasting insecticidal net (LLIN) with the pyrethroid deltamethrin on the sides and deltamethrin plus PBO on the roof and, in the case of the P3-BBnet case, also on the barrier. Comparison of two possible P3 barrier shapes, a short T (above the sleeper's chest, right to left) and a longer, longitudinal 'L' barrier (above the entire sleeper, head to toe) with a standard P3, were performed in a large insectary bioassay at LSTM under simulated natural conditions to accurately measure performance. Results consistently

showed that the longitudinal 'L' barrier variant was significantly more lethal than the T variant and the PermaNet 3 bednet (Fig. 1), giving approximately 30% higher mortality. In partnership with LSTM and Against Malaria Foundation, Vestergaard has produced this BBnet design, which thus represents a variant of the widely-distributed pyrethroid-PBO PermaNet 3. The PermaNet 3-BBnet (P3-BBnet; Fig. 1) is identical to a PermaNet 3 except for the addition of a 40 cm high longitudinal barrier attached to the roof, which is made from the same material and impregnated in the same way as the roof of the PermaNet 3 and has the same WHO-prequalification (PQ) status

(https://extranet.who.int/pqweb/vector-control-product/permanet-30). The current trial will compare the epidemiological effectiveness of P3-BBnets to PermaNet 3.

Figure 1. Left side: Demonstration of enhanced entomological effectiveness of the P3-Bbnet ('L' barrier style) compared to an alternative ('T'-barrier) variant and a PermaNet 3 (P3) for knockdown and killing of pyrethroid resistant *Anopheles gambiae*. Right side P3-Bbnets hanging in situ during a pilot trial in Kinshasa. The upright section suspended above the net is the barrier, which along with the roof of the net contains PBO + pyrethroid, while the sides have pyrethroid only.

1.3 Trial designs for comparative assessment of bednets

Cluster randomised control trials (cRCTs), with cross-sectional surveys of cohorts recruited specifically for malaria testing for the trial, are the gold standard for assessing effectiveness of LLINs. However, such LLIN RCTs are expensive, and also to date have compared new generation nets to standard pyrethroid-only nets as a reference. With increasing deployment of new generation nets, comparisons to standard nets will become less relevant because programmatic decisions will often be between different types of new generation nets, especially in areas of high pyrethroid resistance (WHO 2023). Comparison between new generation nets represents a greater challenge because each is likely to have a substantially greater impact on malaria than standard nets. Consequently, larger study sizes (in terms of numbers of clusters) will be required to achieve statistical power to demonstrate a significant difference. With a typical cRCT design, this will further increase trial costs, and limit wider testing across a range of transmission settings.

1.3.1 Antenatal clinic-based assessment of malaria prevalence

A simpler, pragmatic operationally-embedded approach to evaluate LLINs is to use malaria prevalence rates in pregnant women attending their first Ante-Natal Clinics (ANCs) as a primary trial outcome measure. A review by van Eijk et al. (2015) showing a strong correlation ($r \approx 0.85$) between observed survey prevalence and prevalence in pregnancy. Work in DRC using a Medicins Sans Frontieres-supported programme testing ANC visitors with rapid diagnostic tests produced promising results for using such data as an informative correlate of wider population prevalence (Hellewell et al. 2018). In a large-scale trial in Sud Ubangi province, northern DRC (2020-2023) involving approximately 40% of ANCs province-wide we have applied the MSF model embedded within a programmatic distribution of bednets by Against Malaria Foundation, the DRC national malaria control programme (PNLP), SANRU, and the Sud Ubangi provincial health service. Almost 1.9 million nets were distributed, approximately half of which were pyrethroid-only PermaNet 2 and half PermaNet 3, with randomised allocation to large health zone clusters (N=16). We detected a comparable level of benefit of PermaNet 2 vs PermaNet 3 to a previous successful operationallyembedded cRCT, which used a child cohort for malaria assessment as its primary endpoint (Staedke et al. 2020), but at substantially lower trial cost. The current trial aims to apply the same ANC-based primary endpoint for comparative evaluation of the epidemiological impact of P3-BBnets and PermaNet 3, with a key modification being distribution randomised at a lower level of subdivision (health areas) to allow the enhanced study power required.

1.3.2 Malaria and bednet distributions in DRC

The DRC is among the highest burden malaria countries, with preventative malaria control reliant primarily on LLINs; with IRS (spraying) campaigns rarely attempted to date beyond highly focal commercial activities. Country-wide LLIN distributions occur at the province-level (N=26) on an approximately 3-year rolling basis and increasingly involve new generation nets. Many parts of the country have relatively weak local infrastructure and capacity and transport links are often problematic. Documentation of the insecticide resistance status of DRC vectors is improving (Lynd et al. 2018; Wat'senga et al. 2018, 2020) but remains relatively sparse. However, there is a general pattern of widespread pyrethroid resistance in the major malaria vectors *An. gambiae*, although information on the other dominant malaria vector, *An. funestus*, is extremely limited. Populations of *An. gambiae* in DRC often possess both extreme frequencies of knock down resistance mutations at the pyrethroid target site and metabolic resistance mechanisms, which are at least partially blocked by PBO (Njoroge et al. 2022). *Anopheles funestus* on the other hand are primarily reliant on P450 enzymes and therefore are expected to be more susceptible to the effects of PBO (Barnes et al. 2017). The current trial is embedded within a province-wide distribution of PermaNet 3 (PBO+pyrethroid ITNs) in Haut Katanga province, southern, DRC.

2. Study design

2.1 Overview of the operational cRCT BBnet trial

LSTM have partnered with AMF, Vestergaard, Kinshasa School of Public Health, SANRU and the DRC-PNLP to run a two-armed cRCT in Haut Katanga province (Fig. 2) to compare the performance of the P3-BBnet with PermaNet 3. The trial is allied to a programmatic distribution of approximately 4.5 million insecticide treated nets in quarter 2 2023. The vast majority of the nets are PermaNet 3, with 300,000 P3-BBnets distributed as part of the programme. The trial will use as its primary epidemiological outcome measure malaria prevalence of women tested as they visit their first antenatal clinic (ANC1). ANC1 visitors will receive a rapid diagnostic test for malaria and be provided with artemisinin combination therapy (ACT) treatment if the test is positive. The study team will liaise with staff at the health centres to collect these data from consenting visitors, along with additional information provided by questionnaires to the ANC1 visitors. Anonymous summary health record data will be collected from participating health centres to provide pre-distribution baseline for the study. Cross-sectional surveys will assess the hanging of P3-BBnets and user perceptions, collect a subsample of nets for assessment of physical integrity, chemical content, and insecticide bioavailability, and collect mosquitoes for characterisation of the local vector population, infection and blood meals taken in each species, and insecticide resistance testing. Owing to a very high projected sampling effort required for adequate power, the trial will not include comparative entomological endpoints (i.e. between-arm comparisons of abundance, mosquito *Plasmodium* infection rate). Data collection for the trial is projected to run for a period of up to 5 months.

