2.4 Sample size

Projected sample size requirements for the number of clusters required were evaluated under two designs, the first with equal numbers of P3-BBnet and PermaNet 3 clusters monitored and the

second with a ratio of 0.5 (P3-Bbnet/ PermaNet 3), reflecting the more limited numbers of BBnets available. This second imbalanced design proved more feasible to provide suitable power and is presented. Calculations are applied with required power = 80%; type I error rate = 0.05; coefficient of variation for clustering of 0.30 (approximating that observed in the Sud Ubangi trial). We assume that 25 ANC1 visitors will be recruited on average per month per cluster. A single monitoring periods of 3 consecutive months is planned, giving an average cluster size of at least N=75.

Estimated numbers of clusters for a two-sample proportions test	Compute:	* Accepts numlist (
Cluster randomized design, Pearson's chi-squared test	Group-specific numbers of clusters	
Ho: p2 = p1 versus Ha: p2 != p1	Error probabilities	
	0.05 * Significance level	0.8 * Power ~
Study parameters:		
	Clusters	
alpha = 0.0500	Specify the ratio of the numbers of clusters:	Specify cluster sizes/sample sizes:
power = 0.8000	0.5 * Ratio, K2/K1	Group cluster size and ratio \sim
delta = -0.0000 (difference)		75
$p_1 = 0.2400$ $p_2 = 0.1800$		75 × Control ~
		1 * Ratio, M2/M1
Cluster design:	Allow fractional numbers of clusters and sample sizes	;
$k_{ratio} = 0.5000$	Effect size	
M1 = 75	Proportions	Report effect size as:
M2 = 75	0.24 * Control	Difference
rho = 0.0250		Difference
	0.18 * Experimental ~	0.025 * Intraclass correlation
Estimated numbers of clusters and sample sizes:		
V1 - 1 2	Specify varying cluster sizes	
$K_1 = 42$ $K_2 = 21$	* Coefficient of variation for clus	ter sizes
N1 = 3.150		
N2 = 1,575	Cide a	
	Sides:	
	Iwo-sided test	
	Treat number lists in starred(*) options as parallel	

Figure 5. Screenshot from Stata showing sample size calculation for the primary endpoint (malaria prevalence at ANC1s).

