The base malaria prevalence for Haut Katanga is taken from available malaria indicator survey (MICS) data (Fig. 2), which in Sud Ubangi corresponded closely with the ANC1 rate we observed in the PermaNet 2 arm. In the Sud Ubangi trial analysis, clusters receiving PermaNet 3 exhibited up to 30% lower prevalence than those receiving standard nets. This is assumed to represent the expected effect size for PermaNet 3, i.e. they will act to reduce malaria prevalence by 30% compared to the prevalence rate of 34% from the MICS (Fig. 2). Sample size calculations are based on a projected *additional* effect of P3-BBnets vs P3 of 25%. Therefore, the prevalence projected in each study arm is PermaNet 3 = 0.24 and BBnet = 0.18. The sample size calculation performed in Stata is shown in Fig. 5 and suggests that with these parameters 21 P3-BBnet clusters and 42 PermaNet 3 clusters are required.

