4.1.1 Secondary epidemiological outcome

Malaria cases and RDT-confirmed malaria in the population will be approximated as cases per capita using population size estimates from the distribution team for each health area. These will be obtained from routine DHIS2 data for each heath area for comparison of trends with those from the ANC1 data.

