5.1 Epidemiological data

Data will be analysed as both intention to treat and per protocol, which may be important owing to the likely movement of ANC visitors to health centres not in their health area of residence, which will be recorded as part of ANC questionnaires. The primary outcome will be the prevalence of confirmed malaria from the ANC1 visitor surveys, which will be compared between treatment arms using either a generalized estimating equation or generalized linear mixed model with log link function. Covariables from ANC questionnaires may be incorporated into the models where significant. Owing to the difference in the physical appearance of nets, blinding of data collection is not possible but the study arms and health areas will be given random code numbers prior to analysis to facilitate blinding of statistical analysis.

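### Section 5.1 gives the pre-distribution baseline no role in the primary model; its only covariate rule is optional questionnaire items kept if significant

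*Protocol*

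**What the plan says.** Section 2.1 of the protocol states: "Anonymous summary health record data will be collected from participating health centres to provide pre-distribution baseline for the study". It does not say what the records contain, for which months, or how they will be used. Section 4.1.1 separately draws routine malaria case counts by health area as a secondary outcome: "These will be obtained from routine DHIS2 data for each heath area for comparison of trends" with the ANC1 data. No pre-distribution period is given there. The index lists a subsection on recording periods and baseline data, but the body has none; its 4.1.1 is the secondary outcome.

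Section 5.1 compares the arms on ANC1 prevalence with a GEE or a GLMM and a log link. On covariates it says only: "Covariables from ANC questionnaires may be incorporated into the models where significant". The questionnaire in Appendix E covers age, previous children and stage of pregnancy, but also net use last night and how the barrier is hung.

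Under section 2.5, the BBnet areas came from a random-number draw over 133 eligible areas. Control areas were chosen at random, two for each BBnet area, from the same health zones. Monitoring is a single three-month window.

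**The concern.** Leaving the covariate list to an analysis plan would be unremarkable. Here, however, the protocol states a covariate rule, and the rule points away from the most useful variable. It makes adjustment optional, draws candidates from items measured after the intervention, and keeps them by p-value. Net use and barrier hanging can be consequences of the net received, so adjusting for them could remove part of the effect being estimated. The one measure that randomisation guarantees to be unaffected by the nets, the pre-distribution level in each area, has no stated use.

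At stake are precision and the credibility of the result. With one post-distribution survey, the primary analysis contains no before-after information. If BBnet areas happened to start with more or less malaria, an unadjusted estimate would carry that difference as noise, and readers would have no baseline table by which to judge it.

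**Working it through.** **Inputs.** Section 2.4 gives "required power = 80%; type I error rate = 0.05; coefficient of variation for clustering of 0.30", a two-sided test ("Ho: p2 = p1 versus Ha: p2 != p1"), and the following: "Therefore, the prevalence projected in each study arm is PermaNet 3 = 0.24 and BBnet = 0.18". It assumes 25 women per month for three months, "giving an average cluster size of at least N=75". Figure 5 shows an intraclass correlation of 0.025 and a cluster ratio of 0.5.

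**1. Reproduce the plan's figure.** The pooled prevalence is (0.24 + 0.5 × 0.18)/1.5 = 0.22. Control women needed under individual randomisation:

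[1.96 × √(0.22 × 0.78 × 3) + 0.8416 × √(0.24 × 0.76 + 0.18 × 0.82/0.5)]² / 0.06² = 1,098.

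The design effect is 1 + 74 × 0.025 = 2.85. Control clusters: 1,097.7 × 2.85/75 = 41.7, so 42. BBnet clusters: 20.9, so 21. This agrees with the protocol. Power at 42 and 21 clusters is 80.3%.

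**2. Share of variance between clusters.** The design effect splits into 0.975 within clusters and 75 × 0.025 = 1.875 between. 1.875/2.85 = 66%. Only this part can be reduced by a cluster-level covariate.

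**3. Effect of adjustment.** Let r be the correlation between the baseline measure and the true cluster prevalence at follow-up. The between-cluster part is multiplied by (1 − r²):

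design effect = 0.975 + 1.875 × (1 − r²).

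| r (assumed) | Design effect | Power, 42/21 clusters | Clusters for 80% power |
|---|---|---|---|
| 0 | 2.85 | 80.3% | 42/21 |
| 0.3 | 2.68 | 82.7% | 40/20 |
| 0.5 | 2.38 | 86.9% | 35/18 |
| 0.7 | 1.93 | 92.9% | 29/15 |

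These are large-sample figures that ignore the degrees of freedom spent and take no account of zone group.

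**4. Size of chance imbalance.** With the stated coefficient of variation of 0.30 at prevalence 0.24, the between-cluster SD is 0.072. The chance difference between arms in underlying prevalence has SD 0.072 × √(1/42 + 1/21) = 0.019, about a third of the 0.06 target difference. The probability of a difference of 0.02 or more in either direction is about 30%. Choosing controls within zones lowers this somewhat.

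**5. What the zone matching already does.** Counts in Appendix G, BBnet:PermaNet 3:
- Ruashi-Kampemba 10:20
- Lubumbashi 2:4
- Tshamilemba 3:6
- Kenya 2:4
- Mumbunda 3:6
- Kisanga 1:2

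The ratio is exactly 1:2 in all six groups. Taken separately, Ruashi is 8:10 and Kampemba 2:10, so those two zones balance only when combined.

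**The case against.** The strongest reply is that section 5.1 is silent on baseline adjustment and does not exclude it. Its wording is permissive, it has not yet chosen between GEE and GLMM, and an analysis plan that is not shown may add the term. That stands: a reader might infer that the protocol rules out baseline adjustment, and it does not. What remains is that the one rule it does state would, if followed, leave the baseline out.

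A reader might also infer that the trial already holds a malaria baseline for every centre and is wasting it at no cost. Section 2.1 speaks only of summary health records, and 4.1.1 names no pre-distribution months, so the content and completeness of the baseline are unknown. The gain is also uncertain. Three features of the protocol could make r modest: case rates are approximated with population estimates from the distribution team, section 5.1 expects women to attend clinics outside their home area, and a mass net distribution lies between baseline and outcome. At r = 0.3 the gain is about two points.

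A third tempting inference is that chance imbalance would be mistaken for a net effect, making the trial biased. Under randomisation it is not bias: a model that respects the clusters carries it in the standard error, and the type I error rate is preserved. Finally, matching on zone group already removes differences between groups, so only imbalance within groups is left for the covariate to address.

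**Conclusion.** The point holds as a matter of efficiency and of a poorly chosen covariate rule. The protocol commits to a pre-distribution baseline, gives it no role in section 5.1, and states instead a rule based on post-distribution items and significance. The randomised comparison remains valid and the 42/21 calculation is correct. What is forgone is roughly 2, 7 or 13 points of power at r = 0.3, 0.5 or 0.7, and less if zone group absorbs part of the between-cluster variance. Those figures rest on the protocol's own inputs and on an r that the documents do not supply. Because the design has only 80.3% power and the number of BBnet areas is limited by supply, this is one of the few ways left to gain precision, and it should be taken up before the arms are unblinded to the analyst.

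**What to change.** In section 5.1:

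- Define one cluster-level malaria measure per health area from before the distribution, taken from the section 2.1 records or from DHIS2, with source and months stated. An example is the RDT-confirmed rate in the same calendar months before distribution; matching months matters because section 2.3 reports about twofold seasonal variation.
- Enter it (for instance on the log scale) as a fixed covariate in the primary model, with the six-level Appendix G zone group, whatever their p-values.
- Remove selection by significance from the primary model. Keep net use and barrier hanging out of it; they can be examined in secondary analyses.
- Tabulate the baseline by arm.

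Cost: a few sentences, and 1 + 5 = 6 degrees of freedom among 63 clusters. It also needs a check that the baseline records are complete for all 63 areas, with a stated rule for any gap. If r turns out near zero, the loss is limited to those degrees of freedom.
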